### Purpose of Study

- To determine the influence of chlorhexidine gluconate surgical/topical antiseptic solutions on the bacterial environment of the vagina during hysterectomy and compare that to the effect of standard iodine-based preparations on the same.
  - **Primary Aim:** To determine if chlorhexidine gluconate surgical preparation maintains a lower rate of contamination to the surgical field, as determined by bacterial count at 90 minutes from initial preparation, when compared to iodine based preparation.
  - **Secondary Aims:** To investigate the difference between chlorhexidine gluconate and iodine-based preparations influence on:
    - Rate of contamination at both 30 and 60 minutes from initial preparation.
    - Reducing specific pathogens commonly causing post-operative infection throughout the 90-minute window from preparation.
    - Reducing those pathogens that commonly cause bacterial vaginosis.

### Hypothesis or Research Question

- We hypothesize that the percent of samples considered contaminated by bacterial count at 90 minutes from preparation will be 20% lower in the group that receives chlorhexidine preparation vs povidone-iodine.

- We further hypothesize that this trend will be demonstrated throughout the 30-90 minute time window following vaginal preparation.
- Additionally, we hypothesize chlorhexidine will reduce bacterial counts of pathogens more commonly associated with post operative gynecologic infections better than povidone-iodine.
- Finally, we hypothesize chlorhexidine will clear the pathogens associated with bacterial vaginosis more effectively than povidone-iodine.

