  - Study population: All women 18 years of age or older, who plan to undergo total vaginal, laparoscopically assisted vaginal, total laparoscopic, or robotic-assisted laparoscopic hysterectomy, with or without additional concomitant procedures by a physician at Cincinnati Urogynecology Associates or Tri-State Gynecology Oncology, TriHealth Inc. and will be approached for recruitment in their office or in the pre-operative holding area.
  - Inclusion/Exclusion criteria:
    - Inclusion
      - Adults 18 years of age and older
      - English speaking
      - Undergoing total vaginal, laparoscopic assisted vaginal, total laparoscopic, or robotic-assisted laparoscopic hysterectomy by a physician at Cincinnati Urogynecology Associates or Tri-State Gynecology Oncology TriHealth Inc.

- Concomitant procedures such as vaginal vault suspension, suburethral sling, cystoscopy, enterocele repair, anterior or posterior colporrhaphy, bilateral salpingectomy or salpingoophorectomy, staging procedures, lymph node sampling and other indicated procedures will be included
- Ability to provide consent
- Exclusion
  - Unwillingness to participate in the study
  - Non English speaking
  - Patients that do not undergo a hysterectomy
  - Reported allergy to iodine or chlorhexidine preparation solutions
  - Patients undergoing planned debulking surgery for ovarian, fallopian tube or primary peritoneal cancers
  - Current infection necessitating hysterectomy
  - Active sepsis, pelvic abscess or pelvic inflammatory disease
  - Patient receiving Flagyl for treatment of vaginitis or for surgical prophylaxis during the perioperative period, including day of surgery.
- Sample Size
  - Given the incidence of infection following hysterectomy, a surrogate outcome was felt to be necessary in order to complete the study in a timely fashion. Therefore, using the only published randomized controlled trial, we selected contamination of the field as our outcome measure.
  - Contamination is defined as having >5000 bacteria within a culture.
  - The previous study suggested a 22% difference in bacteria contamination, therefore our sample size was calculated to be 71 patients per arm to

detect a 22% difference in cultures defined as contaminated at 90 minutes from surgical preparation.

- *Power Analysis*
  - Our calculation demonstrated need to enroll 60 patients in each arm based on the following:

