    - A difference of 22% in number of cultures found to have >5,000 bacteria growing 90 minutes from preparation
    - Significance at 0.05
    - Power at 80%
    - Odds ratio was 0.289
    - Assuming an estimated loss rate of 15%, the number of patient enrollment per arm was set to 71, for a total of 142 patients. [Attrition calculation: (60/0.85)]
      - Subjects will be randomized by using a random numbers table and sealed sequential envelopes prepared by an independent statistician. Patients of Cincinnati Urogynecology Associates and Tri-State Gynecology Oncology will have independent randomization schedules.
- **Data Collection**
  - *Primary outcome:*
    - The percent of samples considered contaminated at 90 minutes from preparation between groups.
  - *Secondary Outcomes:*
    - The percent of samples considered contaminated at 30 and 60 minutes from preparation between groups.
    - Number of samples reaching a bacterial load of 100,000 following vaginal preparation at any of the specified time points.
    - The change in bacterial count over time. Specific attention will be given to investigate the following bacteria, most commonly identified in association with postoperative infections:

- *Streptococcus Agalactiae*
- *Staphylococcus aureus*
- *Escherichia Coli*
- *Gardnerella Vaginalis*
- *Enterococcus Faecalis*
- *Bacteroides Fragilis*
- Also included, specific bacteria associated with the condition of bacterial vaginosis:
  - *Gardnerella*
  - *Mobiluncus species*
  - *Prevotella*
  - *Bacteroides*
  - *Peptostreptococcus*
- The number of postoperative infections in each group
- *General Demographic Data*
  - Age, BMI, race, past medical history, home medications, allergies , smoking history, prolapse stage, cancer stage, procedures performed, length of stay, surgical and postoperative complications, and estimated blood loss
- *Data Collection tool*
  - A data collection tool will be utilized
- Please see **Appendix B** for evidence regarding outcome measures
- **Intervention or experimental aspect of the study**
  - *Vaginal preparation*
    - The vaginal scrub will be performed by the OR team according to standard procedures for asepsis within the TriHealth System
    - Solutions:
      - 4% chlorhexidine

- 10% povidone-iodine
- *Sample Collection*
  - Samples will be collected in a standard fashion in the operating room after the patient has been anesthetized

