**(Appendix C)**

- **Statistical Analysis**

The primary outcome is the proportion of contamination (defined as having >5000 bacteria within a culture) at 90 minutes from initial preparation. Logistic regression will be implemented to compare the odds ratio between two groups. Furthermore, multiple logistic regression will be utilized to test for confounding variables. For continuous variable, descriptive statistics will be reported with mean and standard deviation (or median and interquartile range). Difference between two groups will be evaluated in each time point by independent Student's t-test or nonparametric equivalent (Mann Whitney-U test). Alpha < 0.05 will be considered statistically significant.

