  - Therefore, the level of 5,000 is considered a reasonable threshold to utilize as one of contamination.
- *Selection of time window for culture collection*
- In the original pilot study reported by Culligan, samples were collected prior to preparation, then at 30, 90, 150 and 210 minutes. Growth of bacteria dramatically dropped off following the 90 minute cultures. Peak colony counts were identified between 30 and 90 minutes following preparation, suggesting a “weakest link” in standard infection prophylaxis.
  - In the randomized trial reported by Culligan the same trend was reported. Highest contamination levels were seen at within the 30-90 minute window.
  - Literature reporting on the average length of time required to complete a hysterectomy for benign indications varies in reported results:

Study	TVH	TAH	LAVH	TLH	RTLH
Chang	80	XX	118	XX	XX
Johns	63	XX	102	XX	XX

Shashoua	XX	XX	XX	122	142
Ribeiro	78	109	XX	118	XX

- Based on these average times, the window of highest contamination remains within the average length of most benign hysterectomies and therefore provides relevant clinical implication.
  - *Rationale for Inclusion of BV analysis*
    - A prospective case series detailing vaginal cultures from women undergoing benign gynecologic, urogynecologic and gynecology oncology surgeries. The cultures were collected pre-operatively and were analyzed using Nugent criteria. 27% of the women in this study were found to have bacterial vaginosis (BV) at presentation and 36% of these women developed a post-operative infection.
    - Soper, one of the most quoted authors when discussing the relationship of BV and cuff cellulitis reported that patients with BV have a 3x higher risk of developing cuff cellulitis or abscess after abdominal hysterectomy compared to those with healthy vaginal flora.
    - Another large series from the late eighties reported on patients with and without BV undergoing abdominal hysterectomy, and within this population, 35% of women with BV developed a postoperative cuff infection compared with 8% of women without BV.
    - Finally, The American College of Obstetricians and Gynecologists recommends screening for BV prior to performing a hysterectomy to prevent postoperative cuff infections.

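### The clearance and pathogen-reduction hypotheses are tested time point by time point without the time-0 culture, which dilutes the effect; analysing time-0 carriers by arm would be a better secondary analysis

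*Combined protocol and SAP*

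**What the plan says.** Two secondary hypotheses concern named organisms. One is that "we hypothesize chlorhexidine will clear the pathogens associated with bacterial vaginosis more effectively than povidone-iodine". The other is that "we hypothesize chlorhexidine will reduce bacterial counts of pathogens more commonly associated with post operative gynecologic infections better than povidone-iodine". The Secondary Outcomes list names "The change in bacterial count over time", with one list of organisms linked to postoperative infection and another linked to bacterial vaginosis.

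For continuous variables, the Statistical Analysis section says "Difference between two groups will be evaluated in each time point", by Student's t-test or Mann-Whitney. It gives no definition of clearance, estimator of change, baseline term or analysis set for these outcomes. The Power Analysis covers only contamination at 90 minutes.

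Under Sample Collection, every woman has a swab before preparation. The Laboratory Procedure Outline has a colony count and organism identification done on each sample by laboratory personnel blinded to group.

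On how common vaginosis is, Appendix B reports one cited series in which "27% of the women in this study were found to have bacterial vaginosis (BV) at presentation". It also says that a professional college "recommends screening for BV prior to performing a hysterectomy to prevent postoperative cuff infections". The exclusion criteria list "Patient receiving Flagyl for treatment of vaginitis or for surgical prophylaxis during the perioperative period, including day of surgery".

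**The concern.** Clearing an organism, or reducing its count from the starting level, is mainly a question about women who have it before preparation. A comparison of whole arms at 30, 60 or 90 minutes mixes these women with women who were negative at time 0. Most of the latter will have a count of zero whichever solution is used. This has two effects. A real difference among carriers shrinks in proportion to carriage. And the arms will differ by chance in how many carriers they hold, which a cross-sectional test cannot separate from clearance.

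At stake is how two declared hypotheses are read. A non-significant result from a diluted comparison could be reported as no difference between the solutions, although the time-0 culture that would sharpen the comparison is already being collected.

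**Working it through.** **1. The plan's own figure.** A 22-point difference with an odds ratio of 0.289 implies 36% against 14%: (0.14/0.86)/(0.36/0.64) = 0.1628/0.5625 = 0.289. With two-sided alpha 0.05 and 80% power, n = [1.96√(2×0.25×0.75) + 0.842√(0.36×0.64 + 0.14×0.86)]²/0.22² = (1.200 + 0.498)²/0.0484 = 59.6, so 60 per arm. Then 60/0.85 = 70.6, so 71. The stated sample size reproduces, but it is for the primary outcome only.

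**2. Inputs for the organism hypotheses.** From the documents: 60 evaluable women per arm, alpha 0.05. Illustrative: carriage c = 27%, borrowed from the vaginosis series. Assumed, because the documents give no values: clearance of 50% with povidone-iodine and 80% with chlorhexidine; log10 count in women still positive with mean 4 and SD 1, or mean 3 where a 10-fold lower count is assumed; no new growth in time-0 negatives.

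**3. Dilution.** The difference in all women is c times the difference in carriers. Organism still present: 0.27×0.50 = 13.5% against 0.27×0.20 = 5.4%. The difference is 8.1 points, against 30 points in carriers. Expected carriers per arm: 60×0.27 = 16.2 (71×0.27 = 19.2 if nobody is lost).

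**4. Noise from carriage.** The SD of the difference in carrier numbers is √(2×60×0.27×0.73) = √23.65 = 4.86. A gap of five or more carriers has probability of about P(|Z| ≥ 4.5/4.86 = 0.93), about 35%.

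**5. Simulated power of the planned Mann-Whitney test, 60 per arm, 27% carriage.**

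| Assumed effect in carriers | All women | Time-0 carriers |
|---|---|---|
| 50% v 80% cleared | 32% | 41% |
| 50% v 80% cleared, and persisting counts 10-fold lower | 35% | 51% |
| No carrier clears, counts 10-fold lower | 7% | 74% |

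Repeat runs move these by one or two points. With no true effect, rejection stays near 5% in both analysis sets. At 50% carriage the same three rows are about 58% v 65%, 65% v 81%, and 24% to 26% v 95% to 96%.

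**6. Alternatives within the stated plan.** These use assumed clearance pairs of 40% v 62%, 30% v 60% and 40% v 80%, with carriers' log10 counts at mean 5, SD 1 and 27% carriage. A t-test on raw counts in all women has power of about 4% or less. A Mann-Whitney on change from time 0 in all women has only about 6% to 10%. Adding a change score in all women therefore does not solve the problem.

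**7. What restriction to carriers can and cannot buy.** For 50% v 80% clearance at 27% carriage, a two-proportion z-test has about 33% power in all women and 44% in carriers; Fisher's exact test in carriers has about 35%. Women to enrol per arm for 80% power (normal approximation), all-women analysis against carriers-only analysis: 510 v 297 for 40% v 62%; 302 v 156 for 30% v 60%; 129 v 86 for 40% v 80%. All exceed 71.

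**The case against.** The strongest reply is that denominator choice is not the main problem. For clearance, restriction to carriers raises power only from about 32% to 41%. What limits the trial is some 16 carriers per arm, and no wording changes that. This stands. A reader might infer from the 7% against 74% contrast that the stated test can hardly detect any effect. That contrast requires that no carrier clears in either arm, which is not the clearance hypothesis.

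Other points also stand:

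- A reader might infer that most women will lack each listed organism. The 27% is the prevalence of a condition by Nugent criteria in one series. A woman can carry a listed organism without meeting those criteria, and the documents give no carriage rate for any organism.
- A reader might infer that vaginosis is excluded. The criterion removes women receiving Flagyl; untreated vaginosis stays eligible. The screening recommendation is cited as rationale, and nothing says these practices screen. The criterion may lower the share below 27%, by an unknown amount.
- Analysis in all women is the default reading, since the section names no analysis set. Change over time is listed as an outcome, so the baseline is not wholly forgotten, but no estimator follows from it.
- Women negative at time 0 are not irrelevant. The aims cover the whole 90-minute window, and suppressing new growth is part of what an antiseptic does.
- Chance imbalance in carriage does not bias the randomised comparison, and type I error is preserved.

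What the reply does not remove is that the plan never defines clearance and does not use the time-0 culture. The carrier analysis was at least as powerful in every row of the table, and clearly better wherever counts fall among women who remain positive.

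**Conclusion.** The point holds as a cheap improvement to two secondary hypotheses. The stated cross-sectional tests do not target clearance or reduction among women who start with the organism, and they lose some power by including those who do not. At an illustrative 27% carriage with 60 per arm the loss is modest for clearance (32% v 41%), larger if persisting counts also fall (35% v 51%), and severe only if nobody clears (7% v 74%). The carriage rate, clearance rates and count distribution are assumptions; none is given for the listed organisms.

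The documents do not support saying that these hypotheses are untestable, that the planned comparison is biased, or that most women lack each organism. Nor would restriction to carriers give adequate power. The primary analysis is unaffected.

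**What to change.** In the Secondary Outcomes list and the Statistical Analysis section:

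- For each listed organism, and for any listed vaginosis organism taken together, make the main analysis the comparison by randomised arm among women positive for it on the time-0 swab.
- Define the outcomes at 30, 60 and 90 minutes as clearance (organism not recovered) and log10 count, with cleared women given the lowest rank in a Mann-Whitney test.
- Report the number of time-0 carriers in each arm.
- Report organisms newly recovered in time-0 negatives, by arm, as a companion outcome.
- Label these analyses exploratory, give confidence intervals, and state that a non-significant result will not be read as no difference.

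The subset is fixed by a swab taken before preparation and read by blinded staff, so it keeps the randomised comparison.

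The cost is SAP wording only: no new swabs, cultures or patients. The downside is small denominators (about 16 carriers per arm at 27%, fewer for rarer organisms) and visibly wide intervals.

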### **Background**

Although the rate of hysterectomy is declining nationally, it remains the most commonly performed procedure in gynecology. As such, postoperative infection remains the most common complication of surgical procedures in gynecology. Historically, 30-40% of patients undergoing a hysterectomy develop a post-operative infection. The initiation of antibiotic prophylaxis for appropriate surgical procedures was a significant advancement in the prevention of surgical site infection. More than 30 prospective randomized clinical trials demonstrated reduced risk of infection and morbidity following hysterectomy when receiving antibiotic prophylaxis.

Overall incidence of post operative infection remains relatively low, with a recent cross sectional analysis of NSQIP (National Surgical Quality Improvement Program) data reporting 2.7% occurrence for superficial, deep and organ space infections after hysterectomy. Nonetheless, surgical site infections result in significant morbidity, loss of quality of life, higher risk of re-intervention, and increased costs to the patients affected by them^9. Within gynecology oncology, the risk of post operative infection remains as high as 36%. Therefore, initiatives sponsored by the Centers for Disease Control, National Health Service Network, Centers for Medicare and Medicaid Services and the Joint Commission have targeted preventing and ultimately eliminating postoperative surgical site infections as a priority in patient safety efforts.

Antibiotic prophylaxis has been standardized and universally implemented. A remaining variable is the method of aseptic preparation of the vagina with substantial variation of technique being reported even within institutions. This is concerning in light of the fact that most post-hysterectomy wound infections result from ascending spread of vaginal flora. Removing variability and implementation of standardized protocols have shown infection rate reduction at large surgical centers. Establishing which aseptic solution should be implemented within these protocols remains challenging. The most recent Committee Opinion by the American College of Obstetricians and Gynecologists concludes there is insufficient evidence to render a strong recommendation for either povidone-iodine or chlorhexidine as the ideal agent for surgical preparation of the vagina and that further evidence is necessary.

Povidone-iodine solution has been considered the standard for aseptic surgical preparation of the vagina for decades and is the only solution approved by the FDA for vaginal use. There are however specific qualities of the solution that suggest it may be less than ideal for use in the vagina. First, the vagina is not protected by keratinized epithelium and therefore iodine can be absorbed systemically during vaginal preparation. Second, iodine is less effective in low pH environments. Considering the normal vaginal pH is 3.8-4.5, the aseptic properties of iodine are called into question as a vaginal solution. Finally, it has been shown that iodophores are inactivated in the presence of blood. Therefore, by performing surgery and contaminating the prepared field with some quantity of blood, some degree of the desired asepsis is lost. In light of these inadequacies, an alternative agent must be considered.

More contemporary efforts have begun to focus on chlorhexidine as a more ideal agent for aseptic efforts in surgical preparation of the vagina. In 2010, a large, multicentered, randomized trial of patients undergoing clean contaminated surgeries compared post surgical infection rates between those cleansed with chlorhexidine and those with povidine-iodine. They found that chlorhexidine decreased post-operative superficial wound infections by 50%. Only 10% of the study population underwent non-abdominal gynecologic surgery, and the method of their vaginal preparation was not specified. Though this article cannot be cited as

setting the standard for vaginal preparation, it did change the general approach to skin preparation in the United States and helped support the superiority of chlorhexidine as an aseptic solution.

A recent prospective quality improvement study, performed at an academic tertiary care center on patients of the gynecology oncology service undergoing cytoreductive surgery, reported their results after implementing a surgical site infection prevention bundle that involved 5 steps throughout the surgical process from pre-op to wound care. One of these was vaginal preparation with 4% chlorhexidine. Their baseline infection rate was reported as being 20%. Through their efforts, they decreased the post-operative infection rate to 3%. Due to the high baseline infection rate of their population as well as the multiple interventions employed within their bundle, the study provides further evidence of the likely superiority of chlorhexidine.

The only randomized controlled trial performed to date comparing 4% chlorhexidine to povidone-iodine as a vaginal preparation was reported in 2005. Discussing the true incidence of post-operative infection following hysterectomy and the exceedingly high number of participants that would be required to look at actual infection rates, the authors selected a surrogate marker of infection as their primary outcome. They showed that chlorhexidine decreased bacterial colony counts in the vagina 40% more effectively than povidone-iodine thirty minutes from initial aseptic preparation. The study was however underpowered at time points beyond 30 minutes and lacked specific information on pathogens within the reported cultures.

Therefore, the purpose of our study is to use a randomized controlled trial to determine whether chlorhexidine is superior to povidone-iodine as an aseptic solution in the vagina by comparing its effects on bacterial count, change in common pathogens responsible for postoperative infection and colony counts throughout the time course of a hysterectomy.

